### 4.2.2 Important protocol deviations

The number and percentage of participants with at least one IPD, including COVID-19 related IPD, will be summarised following the PDP categories, for each study intervention group and overall.

All IPDs will be also listed for all participants included in the ITT population. All issues reported due to COVID-19 pandemic, regardless of whether the type of issue is considered a protocol deviation or not, will be listed separately.

## 4.2.3 Baseline assessments and other participant-specific characteristics

## 4.2.3.1 Demographics and participant-specific characteristics

All demographic and participant-specific characteristics reported in section 3.2.1 will be presented in summary tables for each study intervention group and overall; age, height, weight and BMI will be summarised descriptively. Only the baseline measurement for height, weight and BMI will be considered. All the other demographic and participant-specific characteristics will be summarised as categorical variables with the number and percentages of participants by categories. Participants recruitment by geographical region and country will be summarised.

All demographic and participant-specific characteristics will be also provided in listings. The tables and the listings will be based on the ITT population.

## 4.2.3.2 Medical history

Medical history as described in section 3.2.2 will be presented in summary tables as number and percentages of participants by System Organ Class (SOC) and Preferred Term (PT) for each study intervention group and overall. Participants with multiple events in the same SOC/PT will be counted only once in that SOC/PT. Participants with events in more than one SOC/PT will be counted once in each of those SOC/PT. Tables will be sorted alphabetically by SOC and PT. The tables will be based on the ITT population.

### 4.2.3.3 **Prior and concomitant medication**

The number and percentage of participants receiving prior or concomitant medication (by ATC4 classification system codes and generic name) will be presented by treatment in separate tables for the ITT population.

A separate table will be presented for participants who take disallowed prior or concomitant medications. Percentages will be calculated relative to the number of participants in the ITT population.

All medications will also be listed by participant for the ITT population.

## 4.2.3.4 COPD history

COPD characteristics at baseline (time since COPD diagnosis; time since COPD symptoms started; time since last COPD exacerbation; total number of COPD exacerbations within previous 12 months prior to screening, including exacerbations resulted in antibiotic treatment, oral steroid treatment, hospitalization; total number of COPD exacerbations within previous 24 months prior to screening; specific diagnosis of COPD, including diagnosis of chronic airway obstruction, diagnosis of emphysema, diagnosis of obstructive chronic bronchitis; COPD status based on GOLD Classification, including presence of chronic symptoms or respiratory failure; other diagnosis of obstructive lung disease, including previous diagnosis of asthma, diagnosis of rhinitis, rhinitis seasonal or all year round) and the CAT score at baseline will be summarised by treatment for the ITT population.

Descriptive summary statistics will be produced for COPD treatments at randomization such as ICS/LABA, LABA/LAMA, ICS/LABA/LAMA.

### 4.2.3.5 Substance usage

Summary statistics will be produced by study intervention group and overall, for substances use for the ITT population.

# 4.2.4 Analysis of primary efficacy endpoint

## 4.2.4.1 Primary analysis of the primary endpoint

The primary efficacy endpoint is the change from baseline in pre-BD FEV1 at Week 12. The primary estimand is a 'Treatment Policy' estimand, as follows: The difference in mean change from baseline in FEV1 at Week 12 (MEDI3506 – placebo) will be estimated using a repeated measures mixed effects analysis of covariance model (see Section 4.1.2), for the ITT population. This will include all available data from all visits up to and including Week 12, irrespective of whether the participant discontinued study intervention or received reliever therapy. Graphical representations of the LSMeans change from baseline and the two-sided 80% CI over time will be provided by study intervention group using the ITT population.

## 4.2.4.2 Supportive analysis of the primary endpoint

As a supportive analysis of the primary endpoint, the MMRM analysis (see Section 4.1.2) will be repeated on the ITT population using data from visits up to and including Week 12, but excluding the data from visits after IP discontinuation. Graphical representations of the LSMeans change from baseline and the two-sided 80% CI over time will be provided by study intervention group using the ITT population.

### 4.2.4.3 Sensitivity analysis of the primary endpoint

As a sensitivity analysis of the primary endpoint, two MMRM analyses (see Section 4.1.2) will be performed on the ITT population: one with eosinophil strata instead of log-transformed eosinophil value and another excluding eosinophils from the fixed effect.

Additionally, a sensitivity analysis will be performed excluding data where the Spirometry Vendor have identified the results to be 'implausible'. The definition of 'implausible' will be documented separately prior to database lock.

## 4.2.4.4 Subgroup analysis for the primary endpoint

For each of the subgroup factors (see Section 3.1.9) a separate MMRM will be fitted using the same covariates as described for the primary analysis in Section 4.2.4.1. Background medication strata will not be a covariate if background medication strata is the subgroup; geographical region will not be a covariate if it is the subgroup; number of COPD exacerbations in last 12 months will not be a covariate if it is the subgroup. Graphical representations of the LSMeans change from baseline and the two-sided 80% CI over time will be provided for each subgroup by study intervention group using the ITT population. A forest plot (displaying the difference in mean change from baseline in FEV1 at Week 12, together with the two-sided 80% CI and reference line at zero) will be produced for all subgroups.

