#### 4.2.1 Rationale for Study Population

Chronic bronchitis by physician assessment of participant disease history (presence of cough and phlegm on most days for  $\geq 3$  months/year for  $\geq 2$  years) and BCSS average score  $\geq 2$  in cough and sputum domains over the 4-week run-in period allow not only the standard definition of chronic bronchitis history to be used to define participants who could benefit, but also to increase the chances of seeing a measurable effect size in BCSS and other symptom related measures. This BCSS inclusion criterion helps to identify those patients with symptomatic mucus hypersecretion most likely to respond to MEDI3506 due to its mechanism of action. However, the ability to score severity of emphysema on CT scan will also allow for

AstraZeneca

analysis of subpopulations of patients with COPD based upon extent of emphysema to further examine the relationship between emphysema and response to MEDI3506.

During the ongoing COVID-19 pandemic, as a result of changed patient behaviour, there has been a significant reduction in exacerbation frequency compared with previous years. Data from the UK suggested a 50% reduction in exacerbation related-hospital admissions compared with pre-pandemic (Tan et al 2020; Alsallakh et al 2021), and a 39% reduction in primary care consultations related to COPD. This picture is replicated in other countries. Leaving the requirement for at least one moderate or severe exacerbation in the previous 12 months unchanged would lead to the exclusion of patients who in previous years would have been included.

In this study, participants are required to have at least one moderate or severe exacerbation in the previous 24 months, as participants with frequent exacerbations have been shown to have an increased symptom burden and likelihood of subsequent exacerbations (Hurst et al 2010), and a history of exacerbation also results in poor outcomes 'rrespective of ICS use and for exacerbation history of  $\geq 1$  moderate exacerbation (Carange) et al 2017). Participants should be clinically stable and free from an exacerbation of COPD for 1 month prior to SV1 and prior to Day 1.

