#### Table 2Secondary objectives and associated endpoints

Objectives	Endpoints
To assess the PK of MEDI3506 in participants with COPD and chronic bronchitis.	Serum MEDI3506 concentration-time profiles during the intervention and follow-up periods.
To assess the immunogenicity of MEDI3506 compared with placebo in participants with COPD and chronic bronchitis.	Anti-drug antibodies during the intervention and follow-up periods.
To assess the effect of MEDI3506 on COPDCompEx event in participants with COPD and chronic bronchitis.	Time to first COPDCompEx event based on the period from baseline to 4 weeks after last dose (Week 28)
To assess the effect of MEDI3506 compared with placebo on respiratory symptoms in participants with COPD and chronic bronchitis.	
 
Change from baseline to Week 12 in:
 
E-RS:COPD
 
Mean BCSS score (over the previous 4 weeks)
 
Cough VAS item
 

To assess the effect of MEDI3506 compared with placebo on disease impact in participants with COPD and chronic bronchitis.	
 
Change from baseline to Week 12 in SGRQ total score
 
Proportion of participants with a decrease in SGRQ total score of ≥ 4 points from baseline to Week 12
 

To assess the effect of MEDI3506 compared with placebo on airway resistance and reactance in participants with COPD and chronic bronchitis.	
 
Change from baseline to Week 12 in AO parameters:
 
R5-R20
 
R5
 
R20
 
AX
 

To evaluate the effect of MEDI3506 compared with placebo on objective cough measures in participants with COPD and chronic bronchitis.	
 
At Week 12, ratio to baseline in:
 
Daily (ie, 24 hour) cough frequency
 
Night time cough frequency
 
Awake time cough frequency
 

To evaluate the effect of MEDI3506 or placebo on lung function by extent of baseline emphysema on CT scan.	
 
Change from baseline in pre-BD and post-BD FEV1 through Week 28
 
Change from baseline in pre-BD and post BD FVC through Week 28
 

Statistical Analysis Plan D9180C00002 - 2.0

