# 1.2 Study design

This is a Phase II, randomized, double-blind, placebo-controlled, proof-of-concept study to assess the efficacy, safety and tolerability of MEDI3506, administered SC Q4W for 7 doses, in participants with moderate or severe COPD receiving standard of care (dual or triple therapy) as maintenance therapy, with a history of  $\geq 1$  moderate or severe acute exacerbation in the previous 24 months while on stable background treatment, and moderate to severe chronic bronchitis, with active sputum and cough symptoms. The intervention period lasts 28 weeks (7 doses).

Approximately 144 participants will be randomized in a 1:1 ratio to placebo or CCI of MEDI3506 SC Q4W, for 7 doses. The randomization will be stratified by CCI

and background medication (includes ICS) (Inhaled Corticosteroids) vs does not include ICS).

There are 3 study periods: screening and run-in; intervention period; and follow-up.

The general study design is summarised in Table 5.

Study Period	Screening / Run-in	Intervention Period				Follow-up	
Visit Number	SV1 and SV2	SV3	SV4 to SV7	SV8	SV9 to SV11	SV12	SV13 and SV14
Study Week	-5 to -1	0	0 to 8	12	16 to 24	28	32 to 36
	Enrolment, Screening, Run-in	Randomization and Dose 1	Doses 2 and 3	Primary Endpoint Assessment and Dose 4	Doses 5 to 7	End of Intervention Visit	Follow-up

Table 5Study Design

R = randomization; SV = study visit.

There will be one sub-study in this trial:

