# 1.3 Number of participants

A sample size of 140 participants (70 participants per arm) will provide 80% power to detect a difference in mean change from baseline in FEV1 at Week 12 of 90 mL (assumed SD of 250 mL) between the 2 randomized groups at a one-sided 10% level of statistical significance. To allow for 2% of participants being ineligible for the primary analysis, approximately 144 participants will be randomized in the study (72 per arm).

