#### CCI

- Smoking status at baseline (current smoker vs former smoker)
- Baseline BCSS based on 14-day average (<median vs ≥median)
- Baseline total SGRQ score (<median vs ≥median)
- Extent of emphysema (< 10% vs  $\ge 10\%$ )
- SARS-CoV-2 using a nucleic acid test (positive at any point vs never positive)
- SARS-CoV-2 using a serology test (negative at baseline and positive at end of study vs negative at baseline and at end of study).

Analysis for the secondary endpoints (change from baseline through Week 28 in pre-BD and post-BD FEV1, pre-BD and post BD FVC) by extent of emphysema (< 10% vs  $\ge 10\%$ ) will be performed.

Modality of the subgroups will only be explored if there is at least 15% of the total participants in this category.

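### The visible SAP plans emphysema results category by category but specifies no contrast between categories, although the stated purpose is to relate emphysema to response

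*SAP*

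**What the plan says.** SAP Table 2 (and protocol Table 5) lists a secondary objective on "lung function by extent of baseline emphysema on CT scan". Its endpoints are changes in pre- and post-BD FEV1 and FVC through Week 28. Protocol Section 4.2.1 gives the reason for scoring emphysema: "to further examine the relationship between emphysema and response to MEDI3506". Protocol Section 9.4.2.2 leaves the method for this subgroup analysis to the SAP.

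The SAP's provision is one sentence in Section 3.1.9, opening "Analysis for the secondary endpoints (change from baseline through Week 28 in pre-BD and". It names the four endpoints and the 10% cut point but no model. The seven subsections of 4.2.5 on secondary outcomes include none for this objective. In Appendix A, Tables 14.2.1.3.11 to 14.2.1.3.14 are MMRM treatment comparisons by emphysema subgroup and list no between-category estimate.

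The one visible description of a subgroup method is Section 4.2.4.4: "For each of the subgroup factors (see Section 3.1.9) a separate MMRM will be fitted using the same covariates" as the primary analysis, followed by a forest plot of Week 12 treatment differences with 80% CIs. In Section 4.1.2 the only interactions in that model are baseline by visit and treatment by visit.

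**The concern.** Whether response depends on emphysema is a question about the difference between two treatment effects. A plan that yields two effects, each with its own interval and one-sided p-value (Section 4.1.2 makes the p-value a standard MMRM output), leaves the reader to infer that difference. The usual inference is that a drug works in the category with the small p-value and not in the other. That is not a test of effect modification, and at this sample size it often goes wrong.

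The matter has some weight here. Protocol Amendment 4 removed the exclusion for predominant emphysema and added this objective so that response could be examined across all extents of emphysema.

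**Working it through.** **Inputs.** From SAP Section 1.3: "A sample size of 140 participants (70 participants per arm) will provide 80% power" to detect a difference "of 90 mL (assumed SD of 250 mL) between the 2 randomized groups at a one-sided 10% level of statistical significance". Section 1.2 gives 1:1 allocation. Section 3.1.9 sets a floor of 15% of participants for a subgroup category. The documents give no emphysema split, so I assume 50:50 to 85:15, the latter being the floor. I also carry the 90 mL effect and the 250 mL SD into each category and to Week 28. The SAP states them only for the overall Week 12 comparison. No SD is given for FVC, so the figures apply to FEV1.

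**The plan's own figure.** n per arm = 2(1.2816 + 0.8416)² × (250/90)² = 69.6, so 70 per arm and 140 in total. Allowing 2%: 70/0.98 = 71.4, so 72 per arm and 144 randomized. Both agree with the SAP; there is no arithmetic error.

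**Formulas** (normal approximation, n₁ and n₂ being the per-arm sizes of the two categories):

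- SE of the treatment effect in category i: SEᵢ = 250 × √(2/nᵢ)
- Power in category i at one-sided 10%: pᵢ = Φ(90/SEᵢ − 1.2816)
- Exactly one category significant: p₁(1 − p₂) + p₂(1 − p₁); the categories hold different participants, so the estimates are treated as independent
- SE of the contrast: √(SE₁² + SE₂²); 80% half-width = 1.2816 × that SE

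**Worked case, 50:50.** n₁ = n₂ = 35. SEᵢ = 250 × √(2/35) = 59.8 mL. pᵢ = Φ(90/59.8 − 1.2816) = 0.589. Exactly one significant: 2 × 0.589 × 0.411 = 0.484. Contrast SE = √2 × 59.8 = 84.5 mL; half-width = 108 mL.

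| Split | Power in each category | Exactly one significant, same 90 mL effect in both | Contrast SE (mL) | 80% half-width (mL) |
|---|---|---|---|---|
| 50:50 | 59% / 59% | 48% | 84.5 | 108 |
| 60:40 | 64% / 53% | 49% | 86.3 | 111 |
| 70:30 | 69% / 45% | 52% | 92.2 | 118 |
| 80:20 | 73% / 37% | 56% | 105.6 | 135 |
| 85:15 | 75% / 32% | 59% | 118.3 | 152 |

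The SE of the overall effect is 250 × √(2/70) = 42.3 mL, so the contrast is 2.0 to 2.8 times less precise. Its power against a true 90 mL difference between categories, at one-sided 10%, is Φ(90/84.5 − 1.2816) = 41% at 50:50, falling to 30% at 85:15.

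**Can Section 4.2.4.4 supply the contrast?** Read as a fit within each level, it gives two effects and no planned comparison. Read as one model per factor with the listed covariates, it contains no emphysema term. Neither reading specifies an estimate of effect modification.

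**The case against.** The strongest reply is that this is a subgroup display and not a decision rule. The emphysema endpoints lie outside the Hochberg family in Section 4.1.1, and no action hangs on significance in either category. The objective speaks of effects by extent of emphysema and does not itself name a difference; that aim comes from the rationale in protocol Section 4.2.1. A contrast with an 80% half-width of at least 108 mL, wider than the 90 mL design effect, may seem of little use. All of this is fair. It limits how the contrast may be used, but it does not remove the case for showing it.

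Several stronger readings are tempting, and the documents do not support them:

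- **That the trial never estimates the difference.** The SAP amendment history places emphysema subgroup text in Sections 3.1.9, 4.2.5.1, 4.2.5.3 and 4.2.8.2. The last is fully redacted and the others have gaps. The abbreviation list also includes SIDES, a differential-effect search method that no visible section describes. Only the absence from the visible text can be asserted.
- **That this objective is analysed by separate fits within levels.** Section 4.2.4.4 is headed for the primary endpoint and speaks of a model per factor, not per level. For the Week 28 endpoints the model is simply not stated.
- **That comparing significance is the only way to read the output.** Effects with 80% CIs are planned. From two separate fits a reader could take the difference and combine the SEs. That would still be a post hoc calculation and not a planned result.
- **That emphysema as such used to exclude participants.** Amendment 4 removed an exclusion for predominant emphysema only.
- **That subgroup fits would break down under 36 covariance parameters.** That count belongs to the eight pre-BD visits through Week 28. The post-BD endpoints have two post-baseline visits and three parameters, and Section 4.1.2 allows simpler structures if the model does not converge.

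**Conclusion.** The point holds as a gap in the visible specification, not as an error in design or arithmetic. The stated purpose is to relate emphysema to response, yet the released SAP gives no model for these endpoints and no treatment-by-emphysema term or contrast. With an identical 90 mL effect in both categories, about half of trials (48% to 59%) would show exactly one significant category. That range rests on 140 evaluable participants, an SD of 250 mL within categories and at Week 28, and the assumed splits. It ignores both missing data and any precision gained from covariates. It describes how easily the output could be misread; the SAP does not say that anyone will apply such a rule.

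**What to change.** In Section 3.1.9 or a new subsection of 4.2.5, for pre- and post-BD FEV1 and FVC through Week 28, specify one MMRM on the ITT population. To the Section 4.1.2 model add emphysema category, category by visit, treatment by category, and treatment by category by visit. Report the treatment difference in each category and, at Week 28, the difference between them with its two-sided 80% CI, labelled descriptive. Settle the text before the Primary Analysis, because SAP Section 4 has sponsor personnel unblinded at that point.

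Do not carry a single contrast over to the other subgroup factors as a rule. Race, BMI and region have several levels and no single difference, and the SARS-CoV-2 factors are defined after randomization.

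In the same edit, reconcile Appendix A: Tables 14.2.1.3.11 and 14.2.1.3.12 share a pre-BD FEV1 title, and no post-BD FEV1 table by emphysema is listed although it is a named endpoint.

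The cost is SAP wording and modest programming, with no new data. The downside is an openly imprecise estimate (SE about 85 to 118 mL) that cannot show absence of a difference, and the report should say so. Label: cheap improvement.

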### 4.2.4.5 Secondary analysis of the primary endpoint

The secondary analysis of the primary endpoint will consist of repeating the MMRM analysis (see Section 4.1.2) on the ITT population from visits up to and including Week 36.

The observed values and absolute change from baseline though Week 36 will be summarised.

Graphical representations of the LSMeans change from baseline and the two-sided 80% CI over time will be provided by study intervention group using the ITT population.

## 4.2.5 Secondary outcome variables

### 4.2.5.1 Time to first COPDCompEx event

Time to first COPDCompEx event based on the period from baseline to 4 weeks after last dose (Week 28) will be analysed using a Cox proportional hazard model, as described in Section 4.1.6. The data will also be displayed in a Kaplan-Meier plot.

CI

COPDCompEx event data, including date of event and time from the first study intervention administration to event, will be listed by participant for the ITT population, as well as the details of each criteria leading to COPDCompEx event.

#### 4.2.5.2 Analysis of E-RS: COPD score

Change from baseline to Week 12 in E-RS:COPD (total and domain scores) over the previous 4 weeks will be analysed using a repeated measures mixed effects analysis of covariance model as described in Section 4.1.2.

CCI	
	For primary analysis, LSMean change from
baseline through Week 12 in E-RS:COPD total	and domain scores will be presented.

A listing including mean results from each of the domain and the mean total E-RS: COPD score will be produced for the ITT population.

#### 4.2.5.3 Analysis of BCSS score

Change from baseline to Week 12 in mean BCSS score over the previous 4 weeks will be analysed using a repeated measures mixed effects analysis of covariance model as described in Section 4.1.2. CCI

baseline through Week 12 in BCSS total and domain scores will be presented.

A listing including results from each of the domain and the total mean BCSS score will be produced for the ITT population.

#### 4.2.5.4 Analysis of Cough VAS score

For primary analysis, LSMean change from baseline through Week 12 in cough VAS average score will be presented.

A listing including average cough VAS score results will be produced for the ITT population.

